The ADAPT-Sepsis is a multi-centre three-arm randomised controlled trial with internal pilot. Participants are randomly allocated using a ratio 1:1:1 to CRP: PCT: Usual care. A computerised minimisation randomisation system was used, created by the Warwick Clinical Trials unit, to randomise participants. The randomisation allocation was made following consent processes and baseline assessments. Stratification factors were (i) sepsis severity (sepsis or septic shock), (ii) recruitment centre and (iii) surgery within the last 72 hours or not.

Primary and secondary outcomes

The primary outcomes are effectiveness outcome of total duration of antibiotics used to 28 days post randomisation and safety outcome of 28 days all-cause mortality. Secondary outcomes include escalation of care/re-admission; infection re-lapse/recurrence; dose of antibiotics; length and level of critical care stay, length of hospital stay, and 90-days all-cause mortality.

Sample size

A total sample size of 2760 would be able to detect both a mean of 1-day reduction in antibiotic use duration (using a mean antibiotic duration of 7 days, a pooled standard deviation of 6 days, 90% power, a significance level of 5%, with a 5% withdrawals rate) and a non-inferiority safety margin of 5.4 % (using a 1-sided significance level of 2.5%, 90% power and 5% withdrawal rate) assuming 28-day mortality is 15%.

Timing of final analysis

The end of the trial is defined when the last recruited participant completed 28-days follow-up post randomisation. Once all the data have been entered onto the database, the data will be fully validated and cleaned after which the database will be locked, and the final analyses will be undertaken.

Timing of outcome assessments

Primary and secondary outcome data will be collected daily from randomisation until hospital discharge. Data will also be collected post hospital discharge up to 28-days post randomisation. All-cause mortality

will be collected at 90 days using linked data. Any SAE's will also be reported up to 28 days post-randomisation.

Reporting of results

All primary and secondary clinical effectiveness outcomes will be reported in an earlier publication, with process of care and health economics outcomes reported in subsequent publications, when all the data are available.

In addition, the sub-study, RISC-sepsis will also be reported in a further publication (and has its own approved statistical analysis plan).

Statistical principles

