randomisation dates and times. In the event that stop dates are unobtainable and thus missing, we will first look to see if the participant either withdrew completely or died. If so, we will use the withdrawal/death date as the stop date to estimate the duration for a particular course of antibiotics. If they did not withdraw or die, then we would impute the duration for that particular course of antibiotics using the mean duration of all antibiotics for the participant.

The SOFA score is to be collected baseline at day 3 and day 7, however, date may not be available on these particular days hence this score would be missing. In this situation, we'll use the value from the day before. If this is not available, then we'll use the value of the day after. If neither are available, then the value for that particular day will be missing.

Additional analyses

The primary analysis looks at the total duration of antibiotic days from randomisation to day 28. However, it is also of interest to assess the duration of antibiotics during the intervention phase only i.e., when the biomarker guidance is in use, and also from randomisation to ICU discharge. Therefore, additional analyses will estimate the treatment effect for the duration of antibiotic days during the intervention phase only and also to the point of ICU discharge. Similarly, we will also estimate the same treatment effects for the daily defined dose (DDD) secondary outcome.

The impact of COVID-19 pandemic on the trial will be assessed on completion of the trial. The baseline demographics and primary outcomes for participants recruited before COVID-19 will be compared to those recruited during COVID-19. The objective is to assess if there is any change in the population considered for the trial. In addition, for participants recruited during the COVID-19 pandemic period, baseline demographics and primary outcomes will be compared for COVID positive versus COVID negative participants. We also perform a sensitivity analysis by dropping COVID positive participants to see if COVID pandemic has an impact on the trial. We will do a sensitivity analysis to account for the non-compliant sites with PCT testing during intervention and follow-up phase. The plan is to run the primary outcome analysis excluding the non-compliant sites and see if any difference between the arms.

Safety

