	Standard care	PCT	CRP	Total	PCT vs. Standard care Adjusted estimate (95% CI)	CRP vs. Standard care Adjusted estimate (95% CI)
Participant discharged alive from treating hospital						
No	n (%)	n (%)	n (%)	n (%)		
Yes	n (%)	n (%)	n (%)	n (%)		
Missing	n (%)	n (%)	n (%)	n (%)		
Discharge location						
Home	n (%)	n (%)	n (%)	n (%)		
Another hospital	n (%)	n (%)	n (%)	n (%)		
Nursing/residential home						
Other	n (%)	n (%)	n (%)	n (%)		
Missing	n (%)	n (%)	n (%)	n (%)		
Participant discharged on a course of systemic (IV/oral/rectal) antibiotics						
No	n (%)	n (%)	n (%)	n (%)		
Yes	n (%)	n (%)	n (%)	n (%)		
Missing	n (%)	n (%)	n (%)	n (%)		
Time from randomisation to discharge						
N	xx.xx	xx.xx	xx.xx	xx.xx		
Mean (SD)	xx.xx	xx.xx	xx.xx	xx.xx		

Median (IQR)	xx.xx	xx.xx	xx.xx	xx.xx	
Missing	xx.xx	xx.xx	xx.xx	xx.xx	

Table 19: Summary of readmission data by treatment arm

	Standard care	PCT	CRP	Total	PCT vs. Standard care Adjusted estimate (95% CI)	CRP vs. Standard care Adjusted estimate (95% CI)
Participant unscheduled readmission						
No	n (%)	n (%)	n (%)	n (%)		
Yes	n (%)	n (%)	n (%)	n (%)		
Missing	n (%)	n (%)	n (%)	n (%)		
Participant readmission to						
Same hospital	n (%)	n (%)	n (%)	n (%)		
Different hospital	n (%)	n (%)	n (%)	n (%)		
Missing	n (%)	n (%)	n (%)	n (%)		
Participant readmitted from						
Home	n (%)	n (%)	n (%)	n (%)		
Another hospital	n (%)	n (%)	n (%)	n (%)		
Nursing/residential home	n (%)	n (%)	n (%)	n (%)		
Other	n (%)	n (%)	n (%)	n (%)		
Missing	n (%)	n (%)	n (%)	n (%)		
Participant required antibiotics as part of reason for readmission or prior to readmission						
No	n (%)	n (%)	n (%)	n (%)		
Yes	n (%)	n (%)	n (%)	n (%)		
Missing	n (%)	n (%)	n (%)	n (%)		
Time from discharge to readmission						
N	xx.xx	xx.xx	xx.xx	xx.xx		
Mean (SD)	xx.xx	xx.xx	xx.xx	xx.xx		
Median (IQR)	xx.xx	xx.xx	xx.xx	xx.xx		
Missing	xx.xx	xx.xx	xx.xx	xx.xx		

SECTION 5 - STUDY OUTCOME DATA

Table 20: Summary of day 3 and day 7 SOFA score by treatment arm

	Standard care	PCT	CRP	PCT vs. Standard care Adjusted mean difference (95% CI)	CRP vs. Standard care Adjusted mean difference (95% CI)
Day 3 SOFA score					
N	xx.xx	xx.xx	xx.xx		
Mean (SD)	xx.xx	xx.xx	xx.xx		
Median (IQR)	xx.xx	xx.xx	xx.xx		
Missing	xx.xx	xx.xx	xx.xx		
Day 7 SOFA score					
N	xx.xx	xx.xx	xx.xx		
Mean (SD)	xx.xx	xx.xx	xx.xx		
Median (IQR)	xx.xx	xx.xx	xx.xx		
Missing	xx.xx	xx.xx	xx.xx		

Primary effectiveness outcome

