Subgroups	Standard care	PCT	CRP	Effect estimate (95% CI)	PCT vs. Standard care	CRP vs. Standard care
	N; mean(sd)	N; mean(sd)	N; mean(sd)		Adjusted interaction effect (95% CI)	Adjusted interaction effect (95% CI)
Community-acquired pneumonia (CAP)						
	1					
	2					
Hospital-acquired pneumonia (HAP)						
	1					
	2					
Urinary tract infection (UTI)						
	1					
	2					
Intra-abdominal infection						
	1					
	2					
Infection with positive blood culture						
	1					
	2					
Severity (SOFA/APACHE II)						
	1					
	2					

ADDITIONAL ANALYSES

Table 25: Summary of total duration of antibiotic treatment during the intervention phase only by treatment group

	Standard care	PCT	CRP	PCT vs. Standard care Adjusted mean difference (95% CI)	CRP vs. Standard care Adjusted mean difference (95% CI)
Duration of antibiotic treatment (days)					
N	xx.xx	xx.xx	xx.xx		
Mean (SD)	xx.xx	xx.xx	xx.xx		
Median (IQR)	xx.xx	xx.xx	xx.xx		
Missing	xx.xx	xx.xx	xx.xx		

Table 26: Summary of total Daily Defined Dose (DDD) from randomisation to 28 days by treatment group

	Standard care	PCT	CRP	PCT vs. Standard care Adjusted mean difference (95% CI)	CRP vs. Standard care Adjusted mean difference (95% CI)
Daily Defined Dose (DDD) to 28 days (days)					
N	xx.xx	xx.xx	xx.xx		
Mean (SD)	xx.xx	xx.xx	xx.xx		
Median (IQR)	xx.xx	xx.xx	xx.xx		
Missing	xx.xx	xx.xx	xx.xx		

Table 27: Summary of total Daily Defined Dose (DDD) during the intervention phase only by treatment group

	Standard care	PCT	CRP	PCT vs. Standard care Adjusted mean difference (95% CI)	CRP vs. Standard care Adjusted mean difference (95% CI)
Daily Defined Dose (DDD)					
N	xx.xx	xx.xx	xx.xx		
Mean (SD)	xx.xx	xx.xx	xx.xx		
Median (IQR)	xx.xx	xx.xx	xx.xx		
Missing	xx.xx	xx.xx	xx.xx		

Table 28: Baseline demographic characteristics comparing pre-COVID participants versus participants recruited during COVID

Characteristic	Pre-COVID	During Covid	Total	P-Value
Age (years)				
N	xx.xx	xx.xx	xx.xx	x.xx
Mean (SD)	xx.xx	xx.xx	xx.xx	
Median (IQR)	xx.xx	xx.xx	xx.xx	
Missing	xx.xx	xx.xx	xx.xx	
Gender				
Male	n (%)	n (%)	n (%)	x.xx
Female	n (%)	n (%)	n (%)	
Missing	n (%)	n (%)	n (%)	
Critical care admission category				
Medical	n (%)	n (%)	n (%)	x.xx
Elective surgical	n (%)	n (%)	n (%)	
Emergency surgical	n (%)	n (%)	n (%)	
Other	n (%)	n (%)	n (%)	
Missing	n (%)	n (%)	n (%)	
Origin				
Emergency department	n (%)	n (%)	n (%)	x.xx
Emergency admissions unit	n (%)	n (%)	n (%)	
Medical ward	n (%)	n (%)	n (%)	

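### The SOFA fill-in rule can put a post-randomisation score into baseline, and Table 20 compares arms on day-3 and day-7 SOFA only among patients who still have a score

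*SAP*

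**What the plan says.** The SAP section Handling missing data introduces the measurement times in one sentence: "The SOFA score is to be collected baseline at day 3 and day 7". It then allows that a score may be unavailable on those days and gives three steps:

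- First: "In this situation, we'll use the value from the day before".
- Second: "If this is not available, then we'll use the value of the day after".
- Otherwise: "If neither are available, then the value for that particular day will be missing".

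No step is restricted to particular time points, and none mentions death or discharge.

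On timing, the Trial design section says: "The randomisation allocation was made following consent processes and baseline assessments". The section Baseline patient characteristics also treats the baseline clinical measures as pre-randomisation. The section Timing of outcome assessments says: "Primary and secondary outcome data will be collected daily from randomisation until hospital discharge".

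Baseline SOFA is tabulated in Table 6 and again in Table 29. The later scores appear in "Table 20: Summary of day 3 and day 7 SOFA score by treatment arm". That shell has N and Missing rows and, for each biomarker arm against standard care, a column for an adjusted mean difference with 95% CI. The Table 24 shell has a severity row naming SOFA and APACHE II.

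**The concern.** Two separate problems follow from the same paragraph.

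**Baseline.** If the baseline score is missing and the day before has none, the rule takes the day after. Baseline assessment precedes allocation, so that value can be a post-randomisation measurement shown as a baseline characteristic. A baseline variable should not be open to influence from the allocated arm, least of all if it might later define a subgroup.

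**Days 3 and 7.** Patients who have died have no score, and patients who have gone home would not be expected to have one. They become missing unless a neighbouring day supplies a value. If that value is from the day before a death, a living score stands for someone who has died. The between-arm difference is then conditional on being alive and still scored, both of which happen after randomisation. High SOFA is worse, so deaths tend to remove the top of the distribution and discharges the bottom. Arms with identical organ function but different discharge or death patterns can therefore show different means.

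The Analysis methods section recognises this hazard, warning that a comparison restricted to survivors may be biased and naming ranked measures that include death. It does so only for antibiotic duration.

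**Working it through.** The SAP gives no SOFA mean, SD, discharge rate or missingness rate, so there is no stated figure to reproduce. The text can be traced directly; the sizes are illustrations on assumed inputs.

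**1. Does the rule reach baseline?** The sentence naming the measurement times is garbled. Three time points (baseline, day 3, day 7) is the natural reading, because baseline SOFA is listed and tabulated. With baseline included, step two permits the day after, and the Trial design section puts baseline before allocation. A post-randomisation value is therefore permitted.

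**2. Size at baseline.** Let *f* be the share of an arm's baseline values taken from the day after, and *e* the arm effect on SOFA that day. The spurious baseline difference is *f* × *e*.

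- *f* = 0.02, *e* = 0.5: 0.02 × 0.5 = 0.01 points.
- *f* = 0.10, *e* = 1.0: 0.10 × 1.0 = 0.10 points.

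Both *f* and *e* are assumed.

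**3. Discharge effect at day 7, true difference zero.** Score X is a rounded gamma variable limited to 0–24, the same in both arms. A health index h = ρ·z(X) + √(1 − ρ²)·ε, with ρ = 0.5 or 0.9, determines who leaves: the lowest fraction p of h is discharged. The artefact is the mean of X among those remaining in the arm with more discharges, minus the same mean in the other arm.

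| Mean (SD) of X | 20% vs 25% discharged | 20% vs 30% | 30% vs 40% |
|---|---|---|---|
| 4 (3) | 0.10 to 0.18 | 0.21 to 0.37 | 0.24 to 0.43 |
| 5 (3) | 0.10 to 0.19 | 0.21 to 0.39 | 0.24 to 0.43 |
| 6 (4) | 0.14 to 0.25 | 0.28 to 0.51 | 0.31 to 0.57 |

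In each cell the lower value is for ρ = 0.5 and the higher for ρ = 0.9. The range is 0.10 to 0.57, always upwards (apparently worse) in the arm with more discharges.

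**4. Death effect, same model.** Mean 5, SD 3, 20% discharged in both arms, and the highest fraction of h removed as deaths:

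- 6% vs 8% dead: −0.07 to −0.12.
- 6% vs 10% dead: −0.13 to −0.23.

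**5. Check with a different mechanism.** Mean 6, SD 4, with logistic death (slope +0.35 per point) and logistic discharge (slope −0.5 per point), calibrated to the stated percentages. Observed means among those left:

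- 7% dead, 40% discharged: 7.04.
- 7% dead, 50% discharged: 7.56. Difference 7.56 − 7.04 = +0.52 for 10 points more discharges.
- 12% dead, 40% discharged: 6.77. Difference 6.77 − 7.04 = −0.27 for 5 points more deaths.

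The two mechanisms agree in direction and approximate size. These runs leave out the day-before and day-after steps, which would recover scores for patients who left only the day before.

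**The case against.** The strongest reply is that little depends on this. SOFA is not among the primary or secondary outcomes in the SAP. Baseline SOFA is not a covariate, since the models adjust for age, gender and the stratification variables. Table 20 is titled a summary and has no p-value column. All of this stands, and it limits the weight of the point.

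The baseline part also rests on a badly worded sentence, and the SAP's intention that baseline be pre-randomisation is clear elsewhere. That makes the correction easier, but the rule as written still permits the opposite. How often it would be used is not documented.

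Selection is partly visible already: Table 20 has N and Missing rows, Tables 12 and 13 report deaths, and Table 18 reports discharge. None of these gives the numbers dead and discharged at day 3 and day 7, which is what a reader of Table 20 needs. A 5-point gap in deaths by day 7 would also be close to the 5.4% margin for 28-day mortality, so the primary safety analysis would address it directly.

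The loss of scores at discharge is an inference. The daily-collection sentence refers to primary and secondary outcome data, and SOFA is not listed as either.

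A reader might infer that a SOFA severity subgroup will be built on post-randomisation values. The documents do not support that. The subgroup list in Analysis methods contains no SOFA subgroup, and the row in Table 24 is a shell entry with no cut-point and no choice between SOFA and APACHE II. The risk arises only if SOFA is used there.

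**Conclusion.** The point holds, with limited reach. As written, the rule permits a post-randomisation SOFA value to be reported as baseline in Tables 6 and 29; on the assumptions shown this shifts the arm comparison by only 0.01 to 0.10 points. Table 20 presents adjusted mean differences among patients still scored, with no rule for death or discharge, and can place a living score on a day of death.

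It would be tempting to conclude that the bias works for or against the biomarker arms. It has no fixed direction: discharges push an arm's mean up by roughly 0.1 to 0.6 points (5 to 10 points more discharged), deaths push it down by roughly 0.1 to 0.3 points (2 to 5 points more dead), and the net sign is unknown. Every input to these sizes is assumed. Nor does the point cast doubt on antibiotic duration, 28-day mortality or any listed secondary outcome; what is exposed is a set of supporting tables.

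**What to change.** - **Baseline.** Rewrite the sentence on measurement times so that the days covered are unambiguous. Fill a missing baseline SOFA only with the last value before randomisation, never the day after.
- **Death.** State that no SOFA value is carried onto or past the day of death.
- **Table 20.** For days 3 and 7, show by arm the numbers dead, discharged and otherwise missing. Keep mean (SD), labelled as conditional on being scored, and remove the between-arm mean difference.
- **If a comparison is wanted.** Rank all randomised participants: discharged alive (best), then SOFA among those in hospital, then dead (worst). This is in line with the global-rank approach the SAP already cites. It is an option, because the ordering involves a judgement of its own.

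The cost is SAP and table-shell wording. Death and discharge timing are already planned for Tables 12, 13 and 18. The downside is a few more missing baseline values and the loss of a familiar effect measure in a supporting table.

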Table 28: Summary of suspected clinically relevant antibiotic related events during inpatient stay (includes events during readmissions)	49

Table 29: Summary of suspected clinically relevant antibiotic related events post hospital discharge to 28 day follow-up.....	50
Table 30: Serious adverse events (SAE) summarised by treatment group	51
Table 31: Assessment of SAE's summarised by treatment group	51

List of Figures

Figure 1: CONSORT diagram	20
--	-----------

SECTION 1 - SCREENING THROUGH TO RANDOMISATION

Figure 1: CONSORT diagram

[figure not shown]

Table 1: Screening of potential participants summarised by recruitment centre

Recruitment Centre	Number screened	Total Number eligible	Total Number Ineligible	Total Number declined	Total Number consented & randomised
	n	n	n	n	n
	n	n	n	n	n
	n	n	n	n	n
	n	n	n	n	n
	n	n	n	n	n
Total:	N	N	N	N	N

Table 2: Randomised participants summarised by recruitment centre and treatment

Recruitment centre	Standard care	PCT	CRP	Total
	n (%)	n (%)	n (%)	n (%)
	n (%)	n (%)	n (%)	n (%)
	n (%)	n (%)	n (%)	n (%)
	n (%)	n (%)	n (%)	n (%)
	n (%)	n (%)	n (%)	n (%)
TOTAL:	N	N	N	N

Table 3: Randomised participants summarised by treatment and randomisation strata

Recruiting centre	Surgery within last 72 hours						No surgery within last 72 hours					
	Sepsis			Septic shock			Sepsis			Septic shock		
	Standard care	PCT	CRP	Standard care	PCT	CRP	Standard care	PCT	CRP	Standard care	PCT	CRP
	n (%)	n (%)	n (%)	n (%)	n (%)	n (%)	n (%)	n (%)	n (%)	n (%)	n (%)	n (%)
	n (%)	n (%)	n (%)	n (%)	n (%)	n (%)	n (%)	n (%)	n (%)	n (%)	n (%)	n (%)
	n (%)	n (%)	n (%)	n (%)	n (%)	n (%)	n (%)	n (%)	n (%)	n (%)	n (%)	n (%)
	n (%)	n (%)	n (%)	n (%)	n (%)	n (%)	n (%)	n (%)	n (%)	n (%)	n (%)	n (%)
	n (%)	n (%)	n (%)	n (%)	n (%)	n (%)	n (%)	n (%)	n (%)	n (%)	n (%)	n (%)
	n (%)	n (%)	n (%)	n (%)	n (%)	n (%)	n (%)	n (%)	n (%)	n (%)	n (%)	n (%)
TOTAL:	N (%)	N (%)	N (%)	N (%)	N (%)	N (%)	N (%)	N (%)	N (%)	N (%)	N (%)	N (%)

SECTION 2 - PARTICIPANT BASELINE AND DEMOGRAPHIC DATA

Table 4: Baseline demographic characteristics of all randomised participants by treatment group

	Standard care	PCT	CRP	TOTAL
Age (years)				
N	xx.xx	xx.xx	xx.xx	xx.xx
Mean (SD)	xx.xx	xx.xx	xx.xx	xx.xx
Median (IQR)	xx.xx	xx.xx	xx.xx	xx.xx
Missing	xx.xx	xx.xx	xx.xx	xx.xx
Gender				
Male	n (%)	n (%)	n (%)	n (%)
Female	n (%)	n (%)	n (%)	n (%)
Missing	n (%)	n (%)	n (%)	n (%)
Critical care admission category				
Medical	n (%)	n (%)	n (%)	n (%)
Elective surgical	n (%)	n (%)	n (%)	n (%)
Emergency surgical	n (%)	n (%)	n (%)	n (%)
Other	n (%)	n (%)	n (%)	n (%)
Missing	n (%)	n (%)	n (%)	n (%)
Origin				
Emergency department	n (%)	n (%)	n (%)	n (%)
Emergency admissions unit	n (%)	n (%)	n (%)	n (%)
Medical ward	n (%)	n (%)	n (%)	n (%)
Surgical ward	n (%)	n (%)	n (%)	n (%)
Another critical care unit	n (%)	n (%)	n (%)	n (%)
Other	n (%)	n (%)	n (%)	n (%)
Missing	n (%)	n (%)	n (%)	n (%)
Core body temperature (°C)				
N	n (%)	n (%)	n (%)	n (%)
Mean (SD)	n (%)	n (%)	n (%)	n (%)
Median (IQR)	n (%)	n (%)	n (%)	n (%)
Missing	n (%)	n (%)	n (%)	n (%)
White cell count (x10⁹/L)				
N	xx.xx	xx.xx	xx.xx	xx.xx
Mean (SD)	xx.xx	xx.xx	xx.xx	xx.xx
Median (IQR)	xx.xx	xx.xx	xx.xx	xx.xx
Missing	xx.xx	xx.xx	xx.xx	xx.xx
Infection acquirement				
Community acquired	n (%)	n (%)	n (%)	n (%)
Hospital acquired	n (%)	n (%)	n (%)	n (%)
Missing	n (%)	n (%)	n (%)	n (%)

Site of infection causing sepsis*				
Respiratory tract	n (%)	n (%)	n (%)	n (%)
If yes above, was it pneumonia	n (%)	n (%)	n (%)	n (%)
If yes above (pneumonia), was it ventilator related	n (%)	n (%)	n (%)	n (%)
Central nervous system	n (%)	n (%)	n (%)	n (%)
Skin and soft tissue	n (%)	n (%)	n (%)	n (%)
Is yes above, was it a surgical site infection	n (%)	n (%)	n (%)	n (%)
Central line related infection	n (%)	n (%)	n (%)	n (%)
Intra-abdominal	n (%)	n (%)	n (%)	n (%)
Urinary tract	n (%)	n (%)	n (%)	n (%)
If yes above, was it associated with a urinary catheter	n (%)	n (%)	n (%)	n (%)
Ear, nose and throat	n (%)	n (%)	n (%)	n (%)
Blood stream	n (%)	n (%)	n (%)	n (%)
If yes above, was it primary	n (%)	n (%)	n (%)	n (%)
Unknown focus	n (%)	n (%)	n (%)	n (%)
Other	n (%)	n (%)	n (%)	n (%)
Is there a causative microorganism identified for the infection causing sepsis				
No	n (%)	n (%)	n (%)	n (%)
Yes	n (%)	n (%)	n (%)	n (%)
Missing	n (%)	n (%)	n (%)	n (%)
Pathogens				
	n (%)	n (%)	n (%)	n (%)
	n (%)	n (%)	n (%)	n (%)

* Each site of infection is summarised separately for all participants. Therefore, it is possible that participants report more than one presumed site of infection causing sepsis.

Table 5: Initial care bundle at baseline summarised by treatment arm

	Standard care	PCT	CRP	TOTAL
Within 3 hours of presentation				
Was lactate level measured				

	No	n (%)	n (%)	n (%)	n (%)
	Yes	n (%)	n (%)	n (%)	n (%)
	Missing	n (%)	n (%)	n (%)	n (%)
Were blood cultures obtained prior to first antibiotics					
	No	n (%)	n (%)	n (%)	n (%)
	Yes	n (%)	n (%)	n (%)	n (%)
	Missing	n (%)	n (%)	n (%)	n (%)
Was intravenous crystalloid fluid administered for hypotension or raised lactate level					
	No	n (%)	n (%)	n (%)	n (%)
	Yes	n (%)	n (%)	n (%)	n (%)
	Missing	n (%)	n (%)	n (%)	n (%)
Were broad spectrum antibiotics administered					
	No	n (%)	n (%)	n (%)	n (%)
	Yes	n (%)	n (%)	n (%)	n (%)
	Missing	n (%)	n (%)	n (%)	n (%)
Was anti-fungal treatment used as part of the 3-hour treatment bundle					
	No	n (%)	n (%)	n (%)	n (%)
	Yes	n (%)	n (%)	n (%)	n (%)
	Missing	n (%)	n (%)	n (%)	n (%)
Was anti-viral treatment used as part of the 3-hour treatment bundle					
	No	n (%)	n (%)	n (%)	n (%)
	Yes	n (%)	n (%)	n (%)	n (%)
	Missing	n (%)	n (%)	n (%)	n (%)
Within 12 hours of presentation					
Source control (e.g. surgical/radiological abscess drainage, vascular line removal)					
	No	n (%)	n (%)	n (%)	n (%)
	Yes	n (%)	n (%)	n (%)	n (%)
	Missing	n (%)	n (%)	n (%)	n (%)
Within 24 hours of presentation					
Was the patient started on systemic steroids (IV or oral)					
	No	n (%)	n (%)	n (%)	n (%)
	Yes	n (%)	n (%)	n (%)	n (%)
	Missing	n (%)	n (%)	n (%)	n (%)

Was the patient put on renal replacement therapy				
	No	n (%)	n (%)	n (%)
	Yes	n (%)	n (%)	n (%)
	Missing	n (%)	n (%)	n (%)

Table 6: Baseline outcome measures

		Standard care	PCT	CRP	TOTAL
qSOFA	N	xx.xx	xx.xx	xx.xx	xx.xx
	Mean (SD)	xx.xx	xx.xx	xx.xx	xx.xx
	Median (IQR)	xx.xx	xx.xx	xx.xx	xx.xx
	Missing	xx.xx	xx.xx	xx.xx	xx.xx
SOFA	N	xx.xx	xx.xx	xx.xx	xx.xx
	Mean (SD)	xx.xx	xx.xx	xx.xx	xx.xx
	Median (IQR)	xx.xx	xx.xx	xx.xx	xx.xx
	Missing	xx.xx	xx.xx	xx.xx	xx.xx
APACHE II	N	xx.xx	xx.xx	xx.xx	xx.xx
	Mean (SD)	xx.xx	xx.xx	xx.xx	xx.xx
	Median (IQR)	xx.xx	xx.xx	xx.xx	xx.xx
	Missing	xx.xx	xx.xx	xx.xx	xx.xx

Table 7: Summary of process data at baseline summarised by treatment arm

		Standard care	PCT	CRP	TOTAL
Time from consent to randomisation (mins)	N	xx.xx	xx.xx	xx.xx	xx.xx
	Mean (SD)	xx.xx	xx.xx	xx.xx	xx.xx
	Median (IQR)	xx.xx	xx.xx	xx.xx	xx.xx
	Missing	xx.xx	xx.xx	xx.xx	xx.xx
Time from hospital admission to randomisation (mins)	N	xx.xx	xx.xx	xx.xx	xx.xx
	Mean (SD)	xx.xx	xx.xx	xx.xx	xx.xx
	Median (IQR)	xx.xx	xx.xx	xx.xx	xx.xx
	Missing	xx.xx	xx.xx	xx.xx	xx.xx
Time from ICU/HDU admission to randomisation					

	N	xx.xx	xx.xx	xx.xx	xx.xx
	Mean (SD)	xx.xx	xx.xx	xx.xx	xx.xx
	Median (IQR)	xx.xx	xx.xx	xx.xx	xx.xx
	Missing	xx.xx	xx.xx	xx.xx	xx.xx
Time from randomisation to first research blood sample taken for the trial					
	N	xx.xx	xx.xx	xx.xx	xx.xx
	Mean (SD)	xx.xx	xx.xx	xx.xx	xx.xx
	Median (IQR)	xx.xx	xx.xx	xx.xx	xx.xx
	Missing	xx.xx	xx.xx	xx.xx	xx.xx
Time from first research blood sample taken for the trial to first research blood sample delivered					
	N	xx.xx	xx.xx	xx.xx	xx.xx
	Mean (SD)	xx.xx	xx.xx	xx.xx	xx.xx
	Median (IQR)	xx.xx	xx.xx	xx.xx	xx.xx
	Missing	xx.xx	xx.xx	xx.xx	xx.xx

SECTION 3 - PARTICIPANT FOLLOW-UP

Table 8: Follow-up rates throughout the trial

Treatment Group	Time-point	Total to reach time point	Completed	Withdrawn completely	Deceased	Incomplete data
Standard Care	Baseline	N	n (%)	n (%)	n (%)	n (%)
	28 days	N	n (%)	n (%)	n (%)	n (%)
	90 days	N	n (%)	n (%)	n (%)	n (%)
PCT	Baseline	N	n (%)	n (%)	n (%)	n (%)
	28 days	N	n (%)	n (%)	n (%)	n (%)
	90 days	N	n (%)	n (%)	n (%)	n (%)
CRP	Baseline	N	n (%)	n (%)	n (%)	n (%)
	28 days	N	n (%)	n (%)	n (%)	n (%)
	90 days	N	n (%)	n (%)	n (%)	n (%)

Table 9: Overall summary of withdrawals by treatment arm*

Withdrawal decision	Withdrawn from intervention only but remains on follow-up			Withdrawn from intervention completely and will not be followed-up		
	Standard care	PCT	CRP	Standard care	PCT	CRP
Participant's decision						
Consultee's decision						
Clinical team decision						
Antibiotics stopped due to futility						
Determined to require long term antibiotics (>21 days) after randomisation						
Other						

* Summary of total number of withdrawal requests i.e. participants may have more than one request

Table 10: Primary cause of death summarised by treatment arm

	Standard care	PCT	CRP	TOTAL	P-value
Sepsis or sepsis related (including organ/multi-organ failure)	n (%)	n (%)	n (%)	N	
Not related to sepsis	n (%)	n (%)	n (%)	N	

Table 11: Number of participant's withdrawing completely throughout the trial

	Standard care	PCT	CRP	TOTAL	P-value
Post-randomisation to ICU discharge	n (%)	n (%)	n (%)	N	
ICU discharge to Hospital discharge	n (%)	n (%)	n (%)	N	
Hospital discharge to 28 day follow-up	n (%)	n (%)	n (%)	N	
28 day follow-up to 90 day follow-up	n (%)	n (%)	n (%)	N	
Overall	n (%)	n (%)	n (%)	N	

Table 12: Number of deaths throughout the trial

	Standard care	PCT	CRP	TOTAL	P-value
Post-randomisation to ICU discharge	n (%)	n (%)	n (%)	N	
ICU discharge to Hospital discharge	n (%)	n (%)	n (%)	N	
Hospital discharge to 28 day follow-up	n (%)	n (%)	n (%)	N	
28 day follow-up to 90 day follow-up	n (%)	n (%)	n (%)	N	
Overall	n (%)	n (%)	n (%)	N	

Table 13: Time from randomisation to death, withdrawal and follow-up summarised by treatment arm

	Standard care	PCT	CRP	PCT vs. Standard care Unadjusted mean difference (95% CI); p-value	CRP vs. Standard care Unadjusted mean difference (95% CI); p-value
Time from randomisation to withdrawing completely from trial					
N	xx.xx	xx.xx	xx.xx		
Mean (SD)	xx.xx	xx.xx	xx.xx		
Median (IQR)	xx.xx	xx.xx	xx.xx		
Missing	xx.xx	xx.xx	xx.xx		
Time from randomisation to death					
N	xx.xx	xx.xx	xx.xx		
Mean (SD)	xx.xx	xx.xx	xx.xx		
Median (IQR)	xx.xx	xx.xx	xx.xx		
Missing	xx.xx	xx.xx	xx.xx		
Time from randomisation to 28- day follow-up					
N	xx.xx	xx.xx	xx.xx		
Mean (SD)	xx.xx	xx.xx	xx.xx		
Median (IQR)	xx.xx	xx.xx	xx.xx		
Missing	xx.xx	xx.xx	xx.xx		
Time from randomisation to 90-day follow-up					
N	xx.xx	xx.xx	xx.xx		
Mean (SD)	xx.xx	xx.xx	xx.xx		
Median (IQR)	xx.xx	xx.xx	xx.xx		

Missing	xx.xx	xx.xx	xx.xx		
---------	-------	-------	-------	--	--

SECTION 4 - INTERVENTION DATA

Table 14: Daily data collection – summary of patient status

	Standard care	PCT	CRP	PCT vs. Standard care Adjusted mean difference (95% CI)	CRP vs. Standard care Adjusted mean difference (95% CI)
Number of days as hospital inpatient					
N	xx.xx	xx.xx	xx.xx		
Mean (SD)	xx.xx	xx.xx	xx.xx		
Median (IQR)	xx.xx	xx.xx	xx.xx		
Missing	xx.xx	xx.xx	xx.xx		
Number of days not a critical care inpatient					
N	xx.xx	xx.xx	xx.xx		
Mean (SD)	xx.xx	xx.xx	xx.xx		
Median (IQR)	xx.xx	xx.xx	xx.xx		
Missing	xx.xx	xx.xx	xx.xx		
Number of days in level 3 unit (ICU)					
N	xx.xx	xx.xx	xx.xx		
Mean (SD)	xx.xx	xx.xx	xx.xx		
Median (IQR)	xx.xx	xx.xx	xx.xx		
Missing	xx.xx	xx.xx	xx.xx		
Number of days level 2 unit (HDU)					
N	xx.xx	xx.xx	xx.xx		
Mean (SD)	xx.xx	xx.xx	xx.xx		
Median (IQR)	xx.xx	xx.xx	xx.xx		
Missing	xx.xx	xx.xx	xx.xx		
Number of days deemed fit for hospital discharge by treating clinical team					
N	xx.xx	xx.xx	xx.xx		
Mean (SD)	xx.xx	xx.xx	xx.xx		
Median (IQR)	xx.xx	xx.xx	xx.xx		
Missing	xx.xx	xx.xx	xx.xx		

Table 15: Summary of blood sampling process by treatment arm

	Standard care	PCT	CRP	Total	PCT vs. Standard care Adjusted estimate (95% CI)	CRP vs. Standard care Adjusted estimate (95% CI)
Duration from the time blood sample taken to the time blood analysis starts (minutes)						
N	xx.xx	xx.xx	xx.xx	xx.xx		
Mean (SD)	xx.xx	xx.xx	xx.xx	xx.xx		
Median (IQR)	xx.xx	xx.xx	xx.xx	xx.xx		
Missing	xx.xx	xx.xx	xx.xx	xx.xx		
Time taken to analyse blood sample (minutes)						
N	xx.xx	xx.xx	xx.xx	xx.xx		
Mean (SD)	xx.xx	xx.xx	xx.xx	xx.xx		
Median (IQR)	xx.xx	xx.xx	xx.xx	xx.xx		
Missing	xx.xx	xx.xx	xx.xx	xx.xx		
Duration of the entire procedure (Sample taken to analysis stop time), (minutes)						
N	xx.xx	xx.xx	xx.xx	xx.xx		
Mean (SD)	xx.xx	xx.xx	xx.xx	xx.xx		
Median (IQR)	xx.xx	xx.xx	xx.xx	xx.xx		
Missing	xx.xx	xx.xx	xx.xx	xx.xx		
Participant had all research blood samples delivered to the laboratory on days a blood sample was taken						
Participants, N	n (%)	n (%)	n (%)	n (%)		
All samples delivered - n (%)	n (%)	n (%)	n (%)	n (%)		
Some missing - n (%)	n (%)	n (%)	n (%)	n (%)		
Of those with some missing above, how many days were missing						
1	n (%)	n (%)	n (%)	n (%)		
2	n (%)	n (%)	n (%)	n (%)		
3	n (%)	n (%)	n (%)	n (%)		
4	n (%)	n (%)	n (%)	n (%)		
5	n (%)	n (%)	n (%)	n (%)		
6	n (%)	n (%)	n (%)	n (%)		
7	n (%)	n (%)	n (%)	n (%)		
8	n (%)	n (%)	n (%)	n (%)		
9	n (%)	n (%)	n (%)	n (%)		

10	n (%)	n (%)	n (%)	n (%)	
13	n (%)	n (%)	n (%)		

Table 16: Summary of advice produced and delivery to the clinical team by treatment arm

	Standard care	PCT	CRP	Total	PCT vs. Standard care Adjusted estimate (95% CI)	CRP vs. Standard care Adjusted estimate (95% CI)
Advice produced and delivered (number of days)						
No. of days	n (%)	n (%)	n (%)	n (%)		
Yes - n (%)	n (%)	n (%)	n (%)	n (%)		
No- n (%)	n (%)	n (%)	n (%)	n (%)		
Missing - n (%)*	n (%)	n (%)	n (%)	n (%)		

* Either the samples weren't processed by the lab or a result had been produced by the lab but it was just not received by the trial/research team

Table 17: Summary of the number of days usual care, stop advice and strong stop advice given at the participant level for those who went into the follow-up phase having received advice by treatment arm

	Standard care	PCT	CRP	PCT vs. Standard care Adjusted estimate (95% CI)	CRP vs. Standard care Adjusted estimate (95% CI)
Usual care advice given, days					
N	xx.xx	xx.xx	xx.xx		
Mean (SD)	xx.xx	xx.xx	xx.xx		
Median (IQR)	xx.xx	xx.xx	xx.xx		
Range	xx.xx	xx.xx	xx.xx		
Stop advice given, days					
N	xx.xx	xx.xx	xx.xx		
Mean (SD)	xx.xx	xx.xx	xx.xx		
Median (IQR)	xx.xx	xx.xx	xx.xx		
Range	xx.xx	xx.xx	xx.xx		
Strong stop advice given, days					
N	xx.xx	xx.xx	xx.xx		
Mean (SD)	xx.xx	xx.xx	xx.xx		

Median (IQR)	xx.xx	xx.xx	xx.xx		
Range	xx.xx	xx.xx	xx.xx		
Stop or Strong stop advice (combined), days					
N	xx.xx	xx.xx	xx.xx		
Mean (SD)	xx.xx	xx.xx	xx.xx		
Median (IQR)	xx.xx	xx.xx	xx.xx		
Range	xx.xx	xx.xx	xx.xx		

Table 18: Summary of discharge data by treatment arm

	Standard care	PCT	CRP	Total	PCT vs. Standard care Adjusted estimate (95% CI)	CRP vs. Standard care Adjusted estimate (95% CI)
Participant discharged alive from treating hospital						
No	n (%)	n (%)	n (%)	n (%)		
Yes	n (%)	n (%)	n (%)	n (%)		
Missing	n (%)	n (%)	n (%)	n (%)		
Discharge location						
Home	n (%)	n (%)	n (%)	n (%)		
Another hospital	n (%)	n (%)	n (%)	n (%)		
Nursing/residential home						
Other	n (%)	n (%)	n (%)	n (%)		
Missing	n (%)	n (%)	n (%)	n (%)		
Participant discharged on a course of systemic (IV/oral/rectal) antibiotics						
No	n (%)	n (%)	n (%)	n (%)		
Yes	n (%)	n (%)	n (%)	n (%)		
Missing	n (%)	n (%)	n (%)	n (%)		
Time from randomisation to discharge						
N	xx.xx	xx.xx	xx.xx	xx.xx		
Mean (SD)	xx.xx	xx.xx	xx.xx	xx.xx		

Median (IQR)	xx.xx	xx.xx	xx.xx	xx.xx	
Missing	xx.xx	xx.xx	xx.xx	xx.xx	

Table 19: Summary of readmission data by treatment arm

	Standard care	PCT	CRP	Total	PCT vs. Standard care Adjusted estimate (95% CI)	CRP vs. Standard care Adjusted estimate (95% CI)
Participant unscheduled readmission						
No	n (%)	n (%)	n (%)	n (%)		
Yes	n (%)	n (%)	n (%)	n (%)		
Missing	n (%)	n (%)	n (%)	n (%)		
Participant readmission to						
Same hospital	n (%)	n (%)	n (%)	n (%)		
Different hospital	n (%)	n (%)	n (%)	n (%)		
Missing	n (%)	n (%)	n (%)	n (%)		
Participant readmitted from						
Home	n (%)	n (%)	n (%)	n (%)		
Another hospital	n (%)	n (%)	n (%)	n (%)		
Nursing/residential home	n (%)	n (%)	n (%)	n (%)		
Other	n (%)	n (%)	n (%)	n (%)		
Missing	n (%)	n (%)	n (%)	n (%)		
Participant required antibiotics as part of reason for readmission or prior to readmission						
No	n (%)	n (%)	n (%)	n (%)		
Yes	n (%)	n (%)	n (%)	n (%)		
Missing	n (%)	n (%)	n (%)	n (%)		
Time from discharge to readmission						
N	xx.xx	xx.xx	xx.xx	xx.xx		
Mean (SD)	xx.xx	xx.xx	xx.xx	xx.xx		
Median (IQR)	xx.xx	xx.xx	xx.xx	xx.xx		
Missing	xx.xx	xx.xx	xx.xx	xx.xx		

SECTION 5 - STUDY OUTCOME DATA

Table 20: Summary of day 3 and day 7 SOFA score by treatment arm

	Standard care	PCT	CRP	PCT vs. Standard care Adjusted mean difference (95% CI)	CRP vs. Standard care Adjusted mean difference (95% CI)
Day 3 SOFA score					
N	xx.xx	xx.xx	xx.xx		
Mean (SD)	xx.xx	xx.xx	xx.xx		
Median (IQR)	xx.xx	xx.xx	xx.xx		
Missing	xx.xx	xx.xx	xx.xx		
Day 7 SOFA score					
N	xx.xx	xx.xx	xx.xx		
Mean (SD)	xx.xx	xx.xx	xx.xx		
Median (IQR)	xx.xx	xx.xx	xx.xx		
Missing	xx.xx	xx.xx	xx.xx		

Primary effectiveness outcome

Table 21: Summary of total duration of antibiotic treatment from randomisation to 28 days by treatment group (Primary outcome)

	Standard care	PCT	CRP	PCT vs. Standard care Adjusted mean difference (95% CI)	CRP vs. Standard care Adjusted mean difference (95% CI)
Duration of antibiotic treatment to 28 days (days)					
N	xx.xx	xx.xx	xx.xx		
Mean (SD)	xx.xx	xx.xx	xx.xx		
Median (IQR)	xx.xx	xx.xx	xx.xx		
Missing	xx.xx	xx.xx	xx.xx		

Primary safety outcome

Table 22: Summary of 28-day all-cause mortality by treatment group (Primary outcome)

	Standard care	PCT	CRP	PCT vs. Standard care Adjusted OR (95% CI)	CRP vs. Standard care Adjusted OR (95% CI)
Mortality status 28 days post randomisation					
Dead	n (%)	n (%)	n (%)		
Alive	n (%)	n (%)	n (%)		
Missing	n (%)	n (%)	n (%)		

Secondary effectiveness and safety outcomes to 28 days

Table 23: Summary of secondary effectiveness and safety outcomes by treatment group

	Standard care	PCT	CRP	PCT vs. Standard care Adjusted estimate (95% CI)	CRP vs. Standard care Adjusted estimate (95% CI)
Mortality status 90 days post randomisation					
Dead	n (%)	n (%)	n (%)		
Alive	n (%)	n (%)	n (%)		
Missing	n (%)	n (%)	n (%)		
Antibiotic dose (Daily Defined Dose)					
N	xx.xx	xx.xx	xx.xx		
Mean (SD)	xx.xx	xx.xx	xx.xx		
Median (IQR)	xx.xx	xx.xx	xx.xx		
Missing	xx.xx	xx.xx	xx.xx		
Patient required unscheduled care escalation					
No	n (%)	n (%)	n (%)		
Yes	n (%)	n (%)	n (%)		
Missing	n (%)	n (%)	n (%)		
Number of unscheduled care escalations					
1	n (%)	n (%)	n (%)		

	2	n (%)	n (%)	n (%)		
	...	n (%)	n (%)	n (%)		
	Total	n	n	n		
	Missing	n (%)	n (%)	n (%)		
Patient had infection relapse/recurrence requiring further antibiotic treatment						
	No	n (%)	n (%)	n (%)		
	Yes	n (%)	n (%)	n (%)		
	Missing	n (%)	n (%)	n (%)		
Number of infection relapses/recurrences						
	1	n (%)	n (%)	n (%)		
	2	n (%)	n (%)	n (%)		
	...	n (%)	n (%)	n (%)		
	Total	n	n	n		
	Missing	n (%)	n (%)	n (%)		
Number of super-infections defined as new infection at a different anatomical site						
	1	n (%)	n (%)	n (%)		
	2	n (%)	n (%)	n (%)		
	...	n (%)	n (%)	n (%)		
	Total	n	n	n		
	Missing	n (%)	n (%)	n (%)		
Time from randomisation to first 'fit' for hospital discharge						
	N	xx.xx	xx.xx	xx.xx		
	Mean (SD)	xx.xx	xx.xx	xx.xx		
	Median (IQR)	xx.xx	xx.xx	xx.xx		
	Missing	xx.xx	xx.xx	xx.xx		

Subgroup analyses

Table 24: Sub-group analyses on the duration of antibiotic days from randomisation to day 28

